10.2.3. Analyses of Secondary Efficacy Endpoints

Frequency counts and percentages will be provided for categorical variables including oral ulcer complete responders at Week 12, and genital ulcer complete responders at Week 12 for subjects who had genital ulcers at baseline. The proportions of complete responders in the two study treatment groups will be compared using a 2-sided Cochran-Mantel-Haenszel (CMH) test with significance level of 0.05, controlling for stratification factors including sex (male, female) and region (Japan, Other). Subjects who have discontinued early prior to Week 12 or who do not have data at Week 12 will be regarded as non-responders at Week 12. A sensitivity analysis using LOCF approach will be performed. The complete response rate based on the approach of NRI, or LOCF or the observed data will be provided for each time point during Placebo-controlled Treatment Phase.

Similarly, the proportion of subjects with no oral ulcers or no genital ulcers following subject's first complete response during Placebo-controlled Treatment Phase will be analyzed. The subjects who have a complete response prior to Week 12 but have no oral ulcers or genital ulcers assessment following subject's first complete response through Week 12 assessment will be excluded when summarizing each endpoint. The treatment comparison will only be conducted if appropriate.

The proportion of subjects achieving an oral ulcer complete response (oral ulcer-free) by Week 6, after the start of dosing, and who remain oral ulcer free for at least 6 additional weeks during the 12-week Placebo-controlled Treatment Phase will be analyzed similarly as the complete response rate as described above. Only those subjects who are oral ulcer-free by Week 6 and remain oral ulcer free for at least 6 consecutive weeks during the 12-week Placebo-controlled Treatment Phase will be considered as a responder; otherwise, subjects will be considered as non-responders. In case an oral ulcer assessment is missing at a visit, the LOCF approach will be used to impute missing assessments up to the ET visit or the last scheduled visit on or prior to date of treatment discontinuation, whichever is later.

The number of oral ulcers following subject's first loss of a complete response will be summarized for subjects who have a complete response prior to Week 12. The number of oral ulcers will be summarized as zero for subjects who had no reappearance of oral ulcers following a complete response prior to Week 12. The comparison between two treatment groups will be performed using ANCOVA model with the treatment, sex and region as factors and baseline number of oral ulcers as a covariate. Within-group LS means, the associated SEs, and treatment differences in LS means, the associated SE, and associated 2-sided 95% CIs and 2-sided p-values will be derived from the model. The treatment comparison will only be conducted if appropriate.

The summary tables with descriptive statistics for number of oral ulcers and general ulcers will be presented by treatment group at all applicable analysis visits.

Summary tables for change from baseline with descriptive statistics will be presented for continuous variables including pain VAS of oral ulcers, pain VAS of genital ulcers, BD Current Activity Form Scores, BD QoL scores, BSAS scores,

, and total score of the Static PGA of skin lesions by treatment group at all applicable visits per study period. For the PGA, only subjects who had BD skin lesions at baseline will be included. For the pain VAS of genital ulcers, only subjects who had genital ulcers at baseline will be included.

The LOCF approach will be used to impute the missing assessment at Week 12 for the following endpoints: pain VAS of oral ulcers, pain VAS of genital ulcers, BD Current Activity Form Scores, BD QoL, and BSAS. The change from baseline at Week 12 (LOCF approach) will be compared between the placebo and the APR 30 BID group using ANCOVA model with change from baseline at Week 12 as the response variable, treatment, sex and region as factors and baseline value as a covariate. Within-group LS means, the associated SEs, and treatment differences in LS means, the associated SE, and associated 2-sided 95% CIs and 2-sided p-values will be derived from the model. A sensitivity analysis for change from baseline in the pain VAS of oral ulcers at Week 12 will be conducted using mixed-effects model for repeated measures (MMRM) with treatment, visit, treatment-by-visit interaction, sex and region as factors and baseline value as a covariate. An unstructured covariance matrix that is homogeneous across treatment groups is to be used.

The frequency distributions for categorical changes from baseline for VAS (-100 to 100 inclusive in 25 increment for each interval) , BD QoL (< -20 to ≥ 10 in 5 increment for each interval), BD BSAS (< -60 to ≥ 40 in 20 increment for each interval)

will be summarized by time point A shift table from baseline to applicable analysis visits will be provided for number of oral ulcers, genital ulcers, the Behçet's disease activity index (0 to 3, 4 to 8 and 9 to 12), and PGA of skin lesions scales components (None, Mild, Moderate, and Severe).

Analyses of time to oral ulcer resolution and time to recurrence of oral ulcers following the first complete response during the Placebo-controlled Treatment Phase will use Kaplan-Meier method to estimate the median resolution/ recurrence time and its 2-sided 95% CIs. The stratified log-rank test will be used for calculating 2-sided p-values for treatment comparison. The hazard ratio and 2-sided 95% CIs will be estimated using a stratified Cox model. For the time to oral ulcer resolution, the baseline number of oral ulcers will be included as covariate in the Cox model. The treatment comparison will only be conducted if appropriate.

Kaplan-Meier curves for time to event endpoints will be provided by treatment group.

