#### **3.2. Secondary Endpoints**

- Complete response rate for oral ulcers at Week 12
  - A complete response is defined as the proportion of subjects who are oral ulcer-free.
- Change from baseline in the pain of oral ulcers as measured by VAS at Week 12
- Complete response rate for genital ulcers at Week 12 for subjects who had genital ulcers at Baseline
  - A complete response is defined as the proportion of subjects who are genital ulcer-free.
- Change from baseline in the pain of genital ulcers, as measured by VAS at Week 12 in subjects who had genital ulcers at baseline
- Change from baseline in disease activity as measured by Behçet's Disease Current Activity scores (BD Current Activity Form) at Week 12
- Change from baseline in the BD QoL score at Week 12
- Change from Baseline in Behçet's Syndrome Activity Score (BSAS) at Week 12
- Time to oral ulcer resolution (complete response), ie, the first instance when a subject has a complete response, during the Placebo-controlled Treatment Phase
- Proportion of subjects with no oral ulcers following complete response, ie, the first time when a subject has a complete response, during the Placebo-controlled Treatment Phase
- Number of oral ulcers following loss of complete response, ie, the first instance when a subject has a reappearance of oral ulcers following a complete response, during the Placebo-controlled Treatment Phase
- Time to recurrence of oral ulcers following loss of complete response, ie, the first instance when a subject has a reappearance of oral ulcers following a complete response, during the Placebo-controlled Treatment Phase
- Change from baseline in the total score of the Static Physician's Global Assessment (PGA) of skin lesions (acne-like lesions, folliculitis and erythema nodosum) of BD at Week 12 in subjects who had BD skin lesions at baseline
- Proportion of subjects achieving an oral ulcer complete response (oral ulcer-free) by Week 6, after start of dosing, and who remain oral ulcer free for at least 6 additional weeks during the 12-week Placebo-controlled Treatment Phase

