4.2.1.2. Secondary Efficacy Endpoints

- Complete response rate for oral ulcers at Week 12

[figure not shown]
- A complete response is defined as the proportion of subjects who are oral ulcer-free.
- Change from baseline in the pain of oral ulcers as measured by visual analog scale (VAS) at Week 12
- Complete response rate for genital ulcers at Week 12 for subjects who had genital ulcers at baseline
 - A complete response is defined as the proportion of subjects who are genital ulcer-free.
- Change from baseline in the pain of genital ulcers, as measured by VAS at Week 12 in subjects who had genital ulcers at baseline
- Change from baseline in disease activity as measured by Behçet's Disease Current Activity scores (BD Current Activity Form [BDCAF]) at Week 12
- Change from baseline in the BD Quality-of-Life (QoL) score at Week 12
- Change from baseline in Behçet's Syndrome Activity Score (BSAS) at Week 12
- Time to oral ulcer resolution (complete response), ie, the first instance when a subject has a complete response, during the Placebo-controlled Treatment Phase
- Proportion of subjects with no oral ulcers following complete response, ie, the first time when a subject has a complete response, during the Placebo-controlled Phase (Note: this will be the proportion of subjects with no oral ulcers following subject's first complete response during the Placebo-controlled Phase.)
- Number of oral ulcers following loss of complete response, ie, the first instance when a subject has a reappearance of oral ulcers following a complete response, during the Placebo-controlled Treatment Phase (Note: this will be the number of oral ulcers reported at the time of the first loss of complete response during the Placebo-controlled Phase.)
- Time to recurrence of oral ulcers following loss of complete response, ie, the first instance when a subject has a reappearance of oral ulcers following a complete response, during the Placebo-controlled Treatment Phase
- Change from baseline in the total score of the Static Physician's Global Assessment (PGA) of skin lesions (acne-like lesions, folliculitis and erythema nodosum) of BD at Week 12 in subjects who had BD skin lesions at baseline
- Proportion of subjects achieving an oral ulcer complete response (oral ulcer-free) by Week 6, after start of dosing, and who remain oral ulcer free for at least 6 additional weeks during the 12-week Placebo-controlled Treatment Phase

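### Rank 12 is labelled as the ulcer count at first loss of complete response, but the SAP tests a zero-filled composite of relapse frequency and ulcer burden, so the label does not describe the result

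*SAP*

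**What the plan says.** **Definition.** Protocol 3.2 lists the secondary endpoint as "Number of oral ulcers following loss of complete response, ie, the first instance when a subject has a reappearance of oral ulcers" after a complete response, during the placebo-controlled phase. SAP 4.2.1.2 repeats this and adds a note: "this will be the number of oral ulcers reported at the time of the first loss of complete response during the Placebo-controlled Phase". SAP Table 4 (section 10.2.1) carries the same label at rank 12 of 14. The ranks form a fixed sequence, each tested at two-sided 0.05.

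**Analysis.** SAP 10.2.3 says the count "will be summarized for subjects who have a complete response prior to Week 12", and that it is "summarized as zero for subjects who had no reappearance of oral ulcers following a complete response prior to Week 12". The arms are then compared on that variable, "performed using ANCOVA model with the treatment, sex and region as factors and baseline number of oral ulcers as a covariate". The paragraph ends: "The treatment comparison will only be conducted if appropriate". No criterion for appropriateness is given.

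**Neighbouring ranks.** Rank 10 is the proportion with no ulcers after the first complete response. Rank 11 is the time to recurrence. For rank 10, SAP 10.2.3 states that responders with no assessment after their "first complete response through Week 12 assessment will be excluded when summarizing each endpoint". For rank 11, SAP 4.2.5 censors such responders at the date of first complete response. The rank 12 paragraph says nothing about them.

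**The concern.** The definition and the analysis describe different variables. A count at first loss of response needs a loss of response and is at least 1. The analysed variable is 0 for every responder before Week 12 who has no recorded reappearance. Neither SAP 4.2.1.2 nor Table 4 mentions the zeros.

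At stake is the meaning of a formally gated claim. Rank 12 could be reported as fewer ulcers after loss of response when the arms differ only in how often response is lost, which ranks 10 and 11 already test. It could also fail when the arms differ clearly in ulcers at relapse. Its result decides whether ranks 13 and 14 are formally tested.

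A second gap concerns responders who clear and are not assessed again. No reappearance is recorded for them, so read literally they receive zero, the best possible score. The general LOCF rule for ulcer-count endpoints in SAP 4.2.5 gives the same value. Three adjacent ranks would then treat the same subjects in three different ways.

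**Working it through.** **The plan's own figure.** The documents give no power or effect size for rank 12. The one stated calculation is for the primary AUC (Protocol 10.3, SAP 4.4: difference 66, SD 144, 102 per group, two-sided 0.05, 90% power). It reproduces: power is 90.5% by the normal approximation and 90.3% by the noncentral t. It has no bearing on rank 12.

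**What the analysed mean is.** Among responders before Week 12, let r be the probability of a recorded reappearance and m the mean count at that reappearance. By definition (SAP 4.2.1.2) the target is m. By analysis (SAP 10.2.3) the mean is r × m + (1 − r) × 0 = r × m.

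**Inputs.** The documents give no responder numbers, relapse rates or counts at relapse for this trial. All of the following are assumptions:
- responders: 85 apremilast and 60 placebo, varied from 60 and 40 to 95 and 80;
- count at relapse: 1 + Poisson(m − 1), independent of the chance of relapse;
- test: two-sample t-test at two-sided 0.05, without covariates, standing in for the ANCOVA;
- 20,000 simulated trials for the zero-filled test and 4,000 for relapsers only.

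**Results with 85 and 60 responders** (apremilast versus placebo):

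| Relapse | m | r × m | Rejects, with zeros | Rejects, relapsers only |
|---|---|---|---|---|
| 60% v 60% | 2 v 2 | 1.20 v 1.20 | 5.0% | 5.2% |
| 50% v 70% | 2 v 2 | 1.00 v 1.40 | 48.4% | 4.8% |
| 40% v 80% | 2 v 2 | 0.80 v 1.60 | 97.6% | 4.9% |
| 60% v 60% | 1.5 v 2.5 | 0.90 v 1.50 | 81.2% | 99.6% |
| 60% v 60% | 2 v 3 | 1.20 v 1.80 | 64.0% | 96.4% |
| 40% v 80% | 3 v 1.5 | 1.20 v 1.20 | 3.2% | 100% |

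Rows 2 and 3 show a significant result from relapse frequency alone. Rows 4 and 5 show that the zero-filled test still responds to burden when relapse rates are equal. Row 6 shows a doubled burden on apremilast that the composite does not see.

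With equal burden, over 60/40 to 95/80 responders and relapse gaps from 60% v 70% to 40% v 80%, the zero-filled test rejects in 12% to 99% of trials. The relapsers-only test stays at about 5%.

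**Is relapsers-only a clean alternative?** No. Take placebo relapse of 70% and counts of 1 + Poisson(1.2), mean 2.20. Suppose apremilast prevents only mild relapses: 25% relapse when the count would be 1, otherwise 70%.
- P(count = 1) = exp(−1.2) = 0.301.
- Apremilast relapse = 0.301 × 0.25 + 0.699 × 0.70 = 0.564.
- Apremilast mean among relapsers = [0.301 × 0.25 × 1 + 0.70 × (2.20 − 0.301)] / 0.564 = 1.404 / 0.564 = 2.49.

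The relapsers-only mean is 0.29 higher on apremilast, although the drug only prevented relapses. With 85 and 65 responders that test rejects in about 25% of simulated trials, in the wrong direction. The 5% rates in the table hold because relapse was simulated as independent of severity.

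**Responders never reassessed.** If u of n responders in an arm have no later assessment and score zero, that arm's mean is multiplied by (1 − u/n). The bias favours the arm with the larger share of such subjects. The simulations do not include them.

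**The case against.** The strongest defence is that the zero rule is the better analysis. It keeps all responders before Week 12, whereas a relapsers-only test conditions on a second post-randomisation event and can mislead, as the mild-relapse example shows. This stands, and it is why the zeros should not simply be deleted. The responder set is itself selected after randomisation, but the zeros add no further selection.

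The rejections in rows 2 and 3 are also not false positives for the hypothesis as analysed, because the zero-filled means truly differ there. Rank 12 is formally tested only if ranks 10 and 11 have succeeded. A reader might infer that the family-wise error rate is broken; the documents do not support that. The fault lies in what the result is called.

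A reader might also infer that rank 12 measures relapse frequency instead of burden, or that everyone who never lost response is scored zero. Both go too far. The score is a product of the two components and responds to burden (rows 4 and 5), and SAP 10.2.3 limits the set to subjects with a complete response before Week 12, so subjects who never cleared receive no zero.

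On unassessed responders, the group is probably small. Ulcers are counted at every visit and at Early Termination (Protocol Table 1), and 100 of 111 Phase 2 subjects completed the double-blind phase and continued (Protocol 1.3). One might also argue that the rank 10 exclusion was meant to cover rank 12. It stands, however, in the paragraph on the proportions free of oral or genital ulcers, and the rank 12 paragraph does not refer to it.

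Finally, the clause that the comparison is made only if appropriate could be read as a safeguard. Without a criterion it does not settle which variable is meant.

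**Conclusion.** The concern holds as a mismatch between the definition and the analysis of a gated endpoint. This rests on the text alone. The labelled quantity is the count at first relapse. The tested quantity is relapse probability times that count, in responders before Week 12. Either component can drive the result, and opposite differences can cancel, so a significant or null rank 12 cannot be read as the label suggests. The handling of responders with no later assessment is inconsistent across ranks 10, 11 and 12, and at rank 12 it gives them the most favourable value.

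Under the assumptions above, equal burden at relapse gives a significant rank 12 in 12% to 99% of trials, depending mainly on the gap in relapse rates. These figures show what the rule can do; they do not predict this trial.

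The impact is limited. The primary test and ranks 2 to 11 are unaffected; only the reading of rank 12 and formal access to ranks 13 and 14 are touched. It should be corrected because the correction is cheap.

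**What to change.** Keep the zero-filled analysis and make the definition match it, before the 12-week database lock:

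1. In SAP 4.2.1.2 and Table 4, rename rank 12 as *number of oral ulcers at first reappearance after complete response, zero if none, in subjects with a complete response before Week 12*. List the departure from the Protocol 3.2 wording in SAP section 14, which now declares no change.
2. State in SAP 10.2.3 that this variable combines relapse frequency with ulcer burden, and that significance does not by itself show fewer ulcers at relapse.
3. Apply the rank 10 exclusion at rank 12 to responders with no ulcer assessment after clearing, and state that the LOCF rule in SAP 4.2.5 does not supply a zero for them.
4. Report the count among relapsers by arm descriptively, without a test, and say that this comparison conditions on a post-randomisation event.

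The cost is SAP wording and a small programming change, with no new data. The downside is slightly fewer subjects at rank 12 and a narrower claim if it succeeds.

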### **4.2. Study Design Rationale**

The design of this study was guided by the results from a Phase 2 study in Behçet's disease ([Section 1.3](#)).

The safety profile of apremilast in Behçet's disease was consistent with its known safety profile as demonstrated in the overall development program.

The primary purpose of the CC-10004-BCT-002 study is to evaluate the efficacy of apremilast in the treatment of mucocutaneous manifestations in subjects with Behçet's disease. The primary endpoint will be the AUC for the number of oral ulcers from Day 1 through Week 12. Oral ulcers have spontaneous flares and remissions; thus, using an AUC for the number of oral ulcers from baseline through Week 12 provides a better representation of the effect of apremilast on the number of oral ulcers the subject experiences during the Placebo-controlled Treatment Phase rather than at one point in time, such as Day 85, the primary endpoint, in the CC-10004-BCT-001 study.

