4.4. Sample Size Determination

The sample size estimation is based on the consideration from the results of the Phase 2 study CC-10004-BCT-001. A 2-sided t-test at a 0.05 significance level will have 90% power to detect a treatment difference of 66 in the AUC of oral ulcer counts from Day 1 through Week 12 (AUC₈₅ of placebo – drug = 66), the primary efficacy endpoint, when the sample size in each group is 102, assuming a common standard deviation of 144.

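### The sensitivity MMRM for oral pain uses one baseline slope for all visits; adding baseline-by-visit would be a cheap, minor improvement

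*SAP*

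**What the plan says.** The rank 2 test (SAP Table 4) is an ANCOVA on LOCF data, "with change from baseline at Week 12 as the response variable, treatment, sex and region as factors and baseline value as a covariate" (SAP 10.2.3). Because it uses Week 12 alone, its baseline slope is a Week 12 slope.

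The same section adds an MMRM as a sensitivity analysis, "with treatment, visit, treatment-by-visit interaction, sex and region as factors and baseline value as a covariate". On the covariance it says: "An unstructured covariance matrix that is homogeneous across treatment groups is to be used". No baseline-by-visit term is listed. Section 10.2.3 names no other sensitivity analysis for this endpoint.

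Protocol Section 5, Table 1, schedules the oral pain VAS after baseline at Weeks 1, 2, 4, 6, 8, 10 and 12. The single slope therefore covers seven visits. On the course of the disease, Protocol 4.2 says: "Oral ulcers have spontaneous flares and remissions".

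**The concern.** Baseline pain may predict pain one week later better than pain twelve weeks later. If so, the slope on baseline changes from visit to visit, and a common slope is a weighted compromise between them. The Week 12 contrast is then adjusted with a slope that does not belong to Week 12, and some of the precision that baseline adjustment should bring is lost.

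The MMRM is there to show whether the pain result depends on LOCF. As specified, it can differ from the ANCOVA in baseline adjustment as well as in missing-data handling, which makes a discrepancy harder to read.

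**Working it through.** **The plan's own figure.** The only stated power is for the primary AUC endpoint (SAP 4.4): "A 2-sided t-test at a 0.05 significance level will have 90% power". The inputs given there are an AUC difference of 66, an SD of 144 and 102 subjects per group. The noncentrality is 66 / (144 × √(2/102)) = 66 / 20.16 = 3.27. The normal approximation gives Φ(3.27 − 1.96) = 90.5%, and the noncentral t gives 90.3%. The figure reproduces. Nothing comparable is stated for pain, so the rest uses assumed values.

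**Inputs.** From the documents: 102 per group, seven visits, the two model specifications. Assumed: correlations of pain with baseline, correlations between visits, and equal SDs at all visits. With equal SDs, the slope of pain on baseline at visit j equals the correlation ρj, and the slope of change is ρj − 1.

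**Formula, complete data.** Let S be the residual covariance across visits given baseline and ρ the vector of visit slopes. The common slope is b = (1′S⁻¹ρ) / (1′S⁻¹1). Relative to a Week 12 slope, the variance of the Week 12 contrast is multiplied by 1 + (ρ12 − b)² / (1 − ρ12²), with baseline variance set to 1.

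**Straight-line fall from Week 1 to Week 12.** Residual correlation between visits was a floor of 0.3-0.5 plus a part that decays by a factor of 0.7-0.9 per week.

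| ρ Week 1 → Week 12 | b | Variance ratio | SE ratio |
|---|---|---|---|
| 0.5 → 0.5 | 0.500 | 1.000 | 1.000 |
| 0.6 → 0.4 | 0.516-0.523 | 1.016-1.018 | 1.008-1.009 |
| 0.6 → 0.3 | 0.485-0.498 | 1.037-1.043 | 1.019-1.021 |
| 0.5 → 0.1 | 0.344-0.362 | 1.060-1.070 | 1.030-1.034 |
| 0.6 → 0.2 | 0.458-0.483 | 1.069-1.084 | 1.034-1.041 |
| 0.7 → 0.3 | 0.573-0.604 | 1.082-1.101 | 1.040-1.049 |
| 0.7 → 0.2 | 0.561-0.615 | 1.136-1.180 | 1.066-1.086 |

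For example, 0.7 → 0.2 with b = 0.561 gives (0.2 − 0.561)² / (1 − 0.04) = 0.130 / 0.96 = 0.136.

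**Other shapes of decay.**
- Exponential decay: correlations of 0.55 at Week 1 and 0.21 at Week 12 give 2.3% on the variance; 0.68 and 0.24 give 6.6%. The latter is 0.25² / (1 − 0.24²) = 0.0625 / 0.942.
- Early plateau: 0.4-0.5 at Week 1, then 0.25-0.30 from Weeks 2-4 onward, gives 0.1-1.0%.

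**Simulation.** 400 runs per scenario, 102 per arm, SD 25 mm, true effect −15 mm, sex and region left out. Drop-out was about 8%; for comparison, the Phase 2 study in Protocol 1.3 lost 11 of 111 subjects (9.9%) by Day 85. Mean SE of the Week 12 contrast in mm:

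| Slopes | Drop-out | Common slope | Baseline-by-visit | LOCF ANCOVA |
|---|---|---|---|---|
| 0.6 → 0.3 | none | 3.400 | 3.345 | 3.345 |
| 0.5 → 0.5 | about 8% | 3.147 | 3.155 | 3.061 |
| 0.6 → 0.4 | about 8% | 3.351 | 3.326 | 3.214 |
| 0.6 → 0.3 | about 8% | 3.528 | 3.464 | 3.344 |
| 0.7 → 0.2 | about 8% | 3.806 | 3.562 | 3.446 |

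With no drop-out, the baseline-by-visit model equals the Week 12 ANCOVA. With equal slopes the extra term costs 3.155 / 3.147 = 1.003, or about 0.3%. Mean MMRM estimates ran from −14.6 to −15.1, and coverage was 94-96%.

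**Splitting the SE gap to the LOCF ANCOVA.** For 0.6 → 0.3 the gap is 3.528 − 3.344 = 0.184, of which 3.528 − 3.464 = 0.064 (35%) is the slope. For 0.7 → 0.2 the gap is 0.360, of which 0.244 (68%) is the slope. The remainder is missing-data handling, since LOCF treats carried-forward values as observed.

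**The case against.** The strongest objection is that the slope drift is assumed. The documents give no pain SD, visit correlations or slopes, and with equal slopes the common slope costs nothing. The Protocol 4.2 sentence on flares concerns ulcers and justifies the AUC endpoint; it does not say how baseline pain predicts later pain. In Phase 2 (Protocol 1.3), ulcer counts on apremilast reached their maximum reduction at Day 15 and stayed low, with pain following a similar course. These are means, not correlations, but they make an early plateau credible, and under a plateau the loss is 1% of variance or less. All of this stands, so the point has to be conditional.

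There is some indirect support for drift. Subjects must have ulcers on the day of randomization (Protocol 7.2), and the VAS asks about the past week (Protocol 6.7.2), so Week 1 pain lies much closer to the qualifying episode than Week 12 pain. That makes drift plausible without measuring it.

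A reader might infer that the Week 12 estimate is biased. It is not, to any material degree: randomization protects the contrast, and the unstructured covariance absorbs the misfit, so coverage holds. In a single trial, a slope error of 0.14-0.25 with a 5 mm baseline imbalance would move the estimate by 0.7-1.25 mm. But that is the same loss already counted in the variance, not an additional one. With SD 25 mm, the baseline difference has SE 25 × √(2/102) = 3.50 mm, so an imbalance of 5 mm or more in either direction has a probability of about 15%.

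A reader might also put the whole SE gap between the MMRM and the ANCOVA down to the slope. With drop-out, even the corrected MMRM has a larger SE than the LOCF ANCOVA, and in the 0.6 → 0.3 case about two thirds of the gap comes from missing-data handling.

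Finally, sex and region effects are also held constant over visits in the MMRM, whereas the ANCOVA estimates them at Week 12. Aligning the baseline term does not make the covariate adjustment identical.

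**Conclusion.** The point holds as a conditional, minor improvement. The single baseline slope is a fact of the specification; a loss of precision follows only if the slope changes between Week 1 and Week 12.

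Under the assumed correlations, the loss in Week 12 variance is about 0-1% with an early plateau and about 1-7% under moderate decay. It is about 15% (13.6-18.0% in the grid) under a steep fall from 0.7 to 0.2, where a Week 1 correlation that high leaves little room for measurement noise. A fall from 0.7 to 0.3 lies between, at 8-10%. On the SE, this is usually a few percent or less.

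The documents do not support saying outright that the model uses a wrong slope or is less precise because of it. Nor do they support any doubt about the rank 2 result. That test is the LOCF ANCOVA; the MMRM is outside the testing sequence in SAP Table 4, so type I error and the rank 2 conclusion do not depend on it.

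**What to change.** Add the baseline-by-visit interaction to the MMRM in SAP 10.2.3 and leave the rest of the model unchanged. This is one term in the model statement: six extra parameters with about 204 subjects, and an SE about 0.3% larger if the slopes are in fact equal. The Week 12 baseline adjustment then corresponds to that of the ANCOVA, and a difference between the two analyses mainly reflects missing-data handling, apart from the sex and region effects noted above.
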